The following group and sub-group names will be used for the statistical analyses:

Group order in tables	Group label in tables	Group definition for footnote
1	30 PreF	30 µg PreF
2	60 PreF	60 µg PreF
3	120 PreF	120 µg PreF
4	Control	Placebo

Some tables might be presented by age category according to the following description:

Sub-group	Sub-group order in tables	Sub-group label in tables	Sub-group definition for footnote
Age	1	18-32Y	18-32 years old subjects
	2	33-45Y	33-45 years old subjects

- **Blinding:** Observer-blind in Epoch 001 and single-blind in Epoch 002.

Table 3 Blinding of study epochs

Study Epochs	Blinding
Epoch 001	observer-blind
Epoch 002	single-blind

- **Sampling schedule:**
 - **Blood samples for haematology/biochemistry** will be collected (~10 mL) from all subjects at Visit 1 (Day 0), Visit 2 (Day 7), Visit 3 (Day 30), Visit 4 (Day 60) and Visit 5 (Day 90).
 - **Blood samples for humoral immune response evaluation** will be collected (~17 mL) from all subjects at Visit 1 (Day 0), Visit 3 (Day 30), Visit 4 (Day 60) and at Visit 5 (Day 90).
 - **Nasal swabs** will be collected from subjects in case of a medically attended respiratory tract infection from enrolment (Visit 1) until study end (Contact 3).
- **Type of study:** self-contained
- **Data collection:** Electronic Case Report Form (eCRF).
- **Safety monitoring:**
 - When the first 25% of subjects (i.e. ~100 subjects; ~25 subjects per study group) have been vaccinated, enrolment will be paused until completion of an unblinded review by a GSK internal Safety Review Committee (iSRC). Continuation of study enrolment will be conditional to a favourable outcome of the iSRC evaluation of all available safety and reactogenicity data collected up to at least 7 days post-vaccination (including Day 7 haematology and biochemistry parameters). In addition, the blinded safety data will be reviewed by GSK Biologicals' Safety Review Team (SRT) on a regular basis throughout the study. Analyses related to iSRC evaluation will be described in a separate document (SAP/TFL for iSRC).

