4.2. Secondary

- Occurrence of AEs from vaccination up to study conclusion:
 - Occurrence of each solicited local and general AE, during a 7-day follow-up period after vaccination (i.e. the day of vaccination and 6 subsequent days), for all subjects in all groups;
 - Occurrence of any unsolicited AE, during a 30-day follow-up period after vaccination (i.e. the day of vaccination and 29 subsequent days), for all subjects in all groups;
 - Occurrence of any haematological (haemoglobin level, White Blood Cells [WBC], lymphocyte, neutrophil, eosinophil and platelet count) and biochemical (alanine amino-transferase [ALT], aspartate amino-transferase [AST] and creatinine) laboratory abnormality at Day 0, Day 7, Day 30, Day 60 and Day 90 for all subjects in all groups;
 - Occurrence of any SAE, for all subjects in all groups.
- Functional antibody titres against RSV for all subjects in all groups:
 - Neutralising antibody titres against RSV-A at Day 0, Day 30, Day 60 and Day 90;
 - Neutralising antibody titres against RSV-B at Day 0, Day 30, Day 60 and Day 90.
- PCA concentration at Day 0, Day 30, Day 60 and Day 90 for all subjects in all groups.
- Humoral immune response to the residual host cell protein NEO in the investigational RSV vaccine at pre-vaccination (Day 0), and 1 month post-vaccination (Day 30) for all subjects in all groups.
 - Antibody concentrations against NEO
- Occurrence of medically attended RSV-associated RTIs up to study conclusion

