The percentage of subjects using **concomitant medication** (any medication, any antipyretic and any antipyretic taken prophylactically) during the 7-day (Day 0 to Day 6) or 30-day (Day 0 to Day 29) follow-up period after vaccination will be summarised by group.

For all subjects in each group and each **haematology and biochemistry** parameter:

- The percentage of subjects having haematology and biochemistry results below or above the local laboratory normal ranges will be tabulated for each timepoint.
- The maximum grading post-vaccination (from Day 7 to Day 90) versus baseline (Day 0) and the percentage of subjects with laboratory parameters above or equal to Grade 1, Grade 2, Grade 3 and Grade 4 will be tabulated (Grades will be based on the FDA Guidance for Industry “Toxicity Grading Scale for Healthy Adult and Adolescent Volunteers Enrolled in Preventive Vaccine Clinical Trials”, see APPENDIX D of the Protocol: FDA toxicity grading scale. Those laboratory parameters not included on FDA Toxicity Grading Scale will not be graded).

Assessment of anti-NEO immune response at Day 30 post-vaccination for each group:

- GMCs pre-and post-vaccination will be tabulated with 95% CI and represented graphically.
- Individual post-vaccination *versus* pre-vaccination results will be plotted using scatter plots. Results of the control group will be used as a reference.
- Geometric mean of ratios of antibody concentrations at Day 30 over pre-vaccination will be tabulated with 95% CI.
- Distribution of the antibody concentrations pre-and post-vaccination and of fold increase after vaccination will be tabulated.

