60 PreF = 60 µg PreF

120 PreF = 120 µg PreF

Control = Placebo

N = number of subjects with available results for the specified laboratory parameter and timing in a given baseline category

n/% = number/percentage of subjects in the specified category

Below = below the normal laboratory range defined for the specified laboratory parameter

Within = within the normal laboratory range defined for the specified laboratory parameter

Above = above the normal laboratory range defined for the specified laboratory parameter

PI(D7) = Post-vaccination at Day 7

PI(D30) = Post-vaccination at Day 30

PI(D60) = Post-vaccination at Day 60

PI(D90) = Post-vaccination at Day 90

Note: For the final analysis, three newly added in-text tables of 'Distribution of change from baseline in ALT, AST and Eosinophil's with respect to normal laboratory ranges (Exposed set)', 'Distribution of change from baseline in Creatinine, Lymphocytes and White Blood Cells (WBC) with respect to normal laboratory ranges (Exposed set)' and 'Distribution of change from baseline in Hemoglobin, Neutrophils and Platelet count with respect to normal laboratory ranges (Exposed set)' will use Template 30.

Template 31 Summary of haematology and biochemistry results by maximum grade from VISIT 2 (D7) up to VISIT 3 (D30) versus baseline (Exposed set)

		VISIT2 (D7) up to VISIT3 (D30)												
		<each group >												
		Unknown			Grade 0		Grade 1		Grade 2		Grade 3		Grade 4	
Laboratory parameter	Baseline PRE(D0)	N	n	%	n	%	n	%	n	%	n	%	n	%
Alanine Aminotransferase (ALT) increase by factor	Unknown													
	Grade 0													
	Grade 1													
	Grade 2													
	Grade 3													
	Grade 4													
	Total													
Aspartate Aminotransferase (AST) increase by factor	...													
Creatinine	...													
Eosinophils increase	...													
Hemoglobin decrease	...													
Lymphocytes decrease	...													
Neutrophils decrease	...													
Platelet count decrease	...													
White Blood Cells (WBC) decrease	...													
White Blood Cells (WBC) increase	...													

<each group>:

30 PreF = 30 µg PreF

60 PreF = 60 µg PreF

120 PreF = 120 µg PreF

Control = Placebo

N = number of subjects with at least one available result for the specified laboratory parameter and follow-up period

n/% = number/percentage of patients reporting at least once the laboratory event when the maximum grading over the follow-up period is considered

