ALT/AST increase by factor: Grade 1 is 1.1-2.5xULN, Grade 2 is 2.6-5.0xULN, Grade 3 is 5.1-10xULN, Grade 4 is >10ULN; ULN is upper limit of the normal range.

Template 32 Summary of haematology and biochemistry results by maximum grade in the specified category from VISIT 2 (D7) up to VISIT 3 (D30) (Exposed set)

Laboratory parameter	Maximum grade	<each group > N =	
		n	%
Alanine Aminotransferase(ALT) increase by factor	Other		
	Grade 2		
	Grade 3		
	Grade 4		
Aspartate Aminotransferase(AST) increase by factor	Other		
	Grade 2		
	Grade 3		
	Grade 4		
Creatinine	Other		
	Grade 2		
	Grade 3		
	Grade 4		
Eosinophils increase	Other		
	Grade 2		
	Grade 3		
	Grade 4		
Hemoglobin decrease	Other		
	Grade 2		
	Grade 3		
	Grade 4		
Lymphocytes decrease	Other		
	Grade 2		
	Grade 3		
	Grade 4		
Neutrophils decrease	Other		
	Grade 2		
	Grade 3		
	Grade 4		
Platelet count decrease	Other		
	Grade 2		
	Grade 3		
	Grade 4		
White Blood Cells (WBC) decrease	Other		
	Grade 2		
	Grade 3		
	Grade 4		
White Blood Cells (WBC) increase	Other		
	Grade 2		
	Grade 3		
	Grade 4		

<each group>:

30 PreF = 30 µg PreF

60 PreF = 60 µg PreF

120 PreF = 120 µg PreF

Control = Placebo

N = number of subjects with the administered dose

n = number of subjects in the specified category

% = n / Number of subjects with available results x 100

Other=all Unknown, Grade 0 and Grade 1

ALT/AST increase by factor: Grade 1 is 1.1-2.5xULN, Grade 2 is 2.6-5.0xULN, Grade 3 is 5.1-10xULN, Grade 4 is >10ULN; ULN is upper limit of the normal range.

Template 33 Summary of haematology change from baseline by maximum grade from VISIT2 (D7) up to VISIT3 (D30) (Exposed set)

	VISIT2 (D7) up to VISIT3 (D30)												
	<each group >												
	Unknown			Grade 0		Grade 1		Grade 2		Grade 3		Grade 4	
Laboratory parameter	N	n	%	n	%	n	%	n	%	n	%	n	%
Hemoglobin (Change from baseline)													

<each group>:

30 PreF = 30 µg PreF

60 PreF = 60 µg PreF

120 PreF = 120 µg PreF

Control = Placebo

N = number of subjects with at least one available result for the specified laboratory parameter and follow-up period

n/% = number/percentage of subjects reporting at least once the laboratory event when the maximum grading over the follow-up period is considered

Hemoglobin (Female) change from baseline value (gm/dL): Grade 1 is any decrease-1.5, Grade 2 is 1.6-2.0, Grade 3 is 2.1-5.0 and Grade 4 is >5.0.

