Template 34 Summary of haematology change from baseline by maximum grade in the specified category from VISIT2 (D7) up to VISIT3 (D30) (Exposed set)

		<each group > N =	
Laboratory parameter	Maximum grade	n	%
Hemoglobin (Change from baseline)	Other		
	Grade 2		
	Grade 3		
	Grade 4		

<each group>:

30 PreF = 30 µg PreF

60 PreF = 60 µg PreF

120 PreF = 120 µg PreF

Control = Placebo

N = number of subjects with the administered dose

n = number of subjects in the specified category

% = n / Number of subjects with available results x 100

Other=all Unknown, Grade 0 and Grade 1

Hemoglobin (Female) change from baseline value (gm/dL): Grade 1 is any decrease-1.5, Grade 2 is 1.6-2.0, Grade 3 is 2.1-5.0 and Grade 4 is >5.0.

**Template 35 Individual results of hemoglobin levels outside of the normal ranges
in < group> (Exposed set)**

PPD

Note: This figure is shown as an example. For the unblinded report, one figure per group will be performed. For the blinded report, 4 graphs will be performed each of them presenting $\frac{PP}{D}$ subjects regardless of treatment (the first $\frac{PP}{D}$ subjects, from the $\frac{PP}{D}$ th to the $\frac{PP}{D}$ th subject...). The X axis will include Day 0, Day 7 and Day 30. The Y axis will be adapted according to each parameter.

Template 36 Number and percentage of subjects with anti-RSV-A neutralising antibody titer equal to or above <cut-off> and GMTs (Per protocol set)

				≥cut-off				GMT					
				n	%	95% CI		value	95% CI		Min	Max	
Antibody	Group	Timing	N			LL	UL		LL	UL			
Anti-RSV-A Neutralizing Antibody	<each group>	PRE											
		PI(D30)											
		PI(D60)											
		PI(D90)											

<each group>:

30 PreF = 30 µg PreF

60 PreF = 60 µg PreF

120 PreF = 120 µg PreF

Control = Placebo

GMT = geometric mean antibody titer calculated on all subjects

N = Number of subjects with available results

95% CI = 95% confidence interval; LL = lower limit, UL = upper limit

n/% = number/percentage of subjects with titer equal to or above specified value

MIN/MAX = Minimum/Maximum

PRE= Pre-vaccination at Day 0

PI(D30) = Post-vaccination at Day 30

PI(D60) = Post-vaccination at Day 60

PI(D90) = Post-vaccination at Day 90

Template 37 Number and percentage of subjects with anti-RSV-A neutralising antibody titer equal to or above <cut-off> and GMTs - by age category (Per protocol set)

Antibody	Group	Sub-Group	Timing	N	≥cut-off				GMT			Min	Max

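### In SAP Amendment 4 the maximum-toxicity-grade table shells (Templates 31–34) cover Day 7 to Day 30, which contradicts the Day 7 to Day 90 window in section 6.3.1.1

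*SAP*

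**What the plan says.** All references are to SAP Amendment 4 unless stated.

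- **Sampling (section 2).** After the Day 0 sample, blood for haematology and biochemistry is taken at "Visit 2 (Day 7), Visit 3 (Day 30), Visit 4 (Day 60) and Visit 5 (Day 90").
- **Endpoint (section 4.2).** The secondary safety endpoint covers any "laboratory abnormality at Day 0, Day 7, Day 30, Day 60 and Day 90 for all subjects in all groups".
- **Analysis text (section 6.3.1.1).** The graded summary is "The maximum grading post-vaccination (from Day 7 to Day 90) versus baseline (Day 0"), with percentages of subjects at or above each of Grades 1 to 4.
- **Shells (section 14, Annex 4).** Template 31 is titled "Summary of haematology and biochemistry results by maximum grade from VISIT 2 (D7) up to VISIT 3 (D30) versus baseline (Exposed set"). Template 32 is the condensed version, "by maximum grade in the specified category from VISIT 2 (D7) up to VISIT 3 (D30) (Exposed set"). Template 33 is "Summary of haematology change from baseline by maximum grade from VISIT2 (D7) up to VISIT3 (D30) (Exposed set"), and Template 34 is its condensed counterpart with the same window. Templates 31 and 33 repeat Day 30 in the column header, and the template list at the start of Annex 4 gives Day 30 for all four.
- **Figure (Template 35).** The note to the individual haemoglobin plot says "The X axis will include Day 0, Day 7 and Day 30", and describes the plot as an example.

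**The concern.** The analysis text and the shells that implement it define different quantities. A maximum over Day 7 to Day 30 is not the maximum over Day 7 to Day 90, and a programmer working from the shells would not produce what section 6.3.1.1 specifies.

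It does not look like one stray title. The Day 30 limit appears in four titles, two column headers and four list entries, and no maximum-grade shell in Annex 4 reaches Day 60 or Day 90. According to section 9, Templates 32 and 34 were introduced by Amendment 3 under changes for the final analysis, when Day 90 data exist. Section 9 records no decision to shorten the window.

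At stake is the severity of late laboratory abnormalities, in a study whose secondary objective (section 3.2) is safety up to study conclusion.

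**Working it through.** The plan gives no figure to reproduce. The check compares windows and then traces a subject through the shells.

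**1. Windows side by side**

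| Place in Amendment 4 | Post-vaccination laboratory visits covered |
|---|---|
| Section 2, sampling | Days 7, 30, 60, 90 |
| Section 4.2, endpoint (abnormality at each day; no mention of grade) | Days 7, 30, 60, 90 |
| Section 6.3.1.1, maximum grade | Day 7 to Day 90 |
| Template 30, below/within/above normal range | Days 7, 30, 60, 90 |
| Templates 31 and 33, title, header and list entry | Day 7 to Day 30 |
| Templates 32 and 34, title and list entry | Day 7 to Day 30 |
| Table added by Amendment 4 (document history) | Day 0 to Day 7 |

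**2. Count**

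Visits required by section 6.3.1.1: 4. Visits inside the shell window: 2. Omitted: 4 − 2 = 2, that is 2/4 = 50% of the scheduled post-vaccination laboratory visits.

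This is a share of visits, not of events. The documents give no laboratory abnormality rates, so the share of graded abnormalities that would be missed cannot be calculated.

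**3. A hypothetical subject**

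Take Grade 0 at Days 7 and 30, Grade 3 at Day 60 and Grade 0 at Day 90.

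- Section 6.3.1.1: max(0, 0, 3, 0) = Grade 3.
- Template 31 as titled: max(0, 0) = Grade 0.
- Template 32 as titled: Other, which pools Unknown, Grade 0 and Grade 1.
- Template 30: out of range at Day 60, with no grade.

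A subject at Grade 2 on Day 30 who reaches Grade 3 on Day 90 would stay at Grade 2 in Templates 31 and 32. The same logic applies to the haemoglobin-change tables (Templates 33 and 34).

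**4. Background from the other SAP documents**

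In Amendment 2 the corresponding shells had Day 30 in the title and Day 90 in the column header; from Amendment 3 both say Day 30. The IDMC SAP runs the same tables from Day 7 to Day 90. The Amendment 2 text is superseded and the IDMC SAP is a separate document, so neither makes the current text wrong. They show that the longer window is feasible and was once in the shells.

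**The case against.** The strongest reply is that the shells do not bind. Annex 4 says mock titles and displays are illustrative and will be adapted as the TFL table of contents indicates. Section 10 leaves the choice of tables per analysis to that document, and section 8.1 ties the final analysis to a TFL dated 01JUN2018 that is not shown. Other shells are plainly not literal. Template 50 is titled Day 30, although section 6.2.1.2 plans Days 30, 60 and 90. Templates 5, 25 and 53 differ between list and shell. Amendment 4 adds a Day 0 to Day 7 grade table that has no shell of its own.

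This stands as far as it goes. A reader might infer that the final-analysis tables stop at Day 30; the documents do not establish that, and section 6.3.1.1 still says Day 90.

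It does not dispose of the contradiction. Where Annex 4 expects the timepoint to vary it usually shows it, with placeholders in Templates 47 and 52 and a note under Template 46; Templates 31–34 have neither. A comparison at a single day can be repeated at other days, but the window of a cumulative maximum defines what is reported. Annex 4 also exempts only editorial or minor changes from a SAP amendment, and going from two visits to four is hard to call either.

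Two further objections are correct and limit the point:

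- The endpoint in section 4.2 concerns abnormality at each day, not maximum grade, and Template 30 serves it through Day 90. The direct conflict is with section 6.3.1.1.
- A reader might infer that late abnormalities vanish from the safety reporting. They do not. Template 30 keeps Days 60 and 90. Section 9 plans individual figures for the Day 90 and final analyses, for haemoglobin beyond Grade 2 and for white cell counts outside the limits. Section 8.1 provides individual listings at the final analysis.

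The Template 35 axis note, marked as an example, is supporting evidence only.

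**Conclusion.** The contradiction is real: Templates 31–34 and their list entries use Day 7 to Day 30 where section 6.3.1.1 specifies Day 7 to Day 90. The consequence is conditional. If the shells are run as titled, 2 of the 4 post-vaccination laboratory visits are left out of every Day 7-onward maximum-grade table, and a Grade 2–4 value first reached at Day 60 or Day 90 is counted as Other or as a lower grade. What would be lost is the tabulated severity, not all trace of the abnormality.

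The size rests on the visit count alone. No number of affected subjects can be given without assuming abnormality rates that the documents do not contain.

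This is a moderate inconsistency in a descriptive secondary safety display. The desirability ranking in section 6.4 uses Day 7 reactogenicity and Day 30 immunogenicity and no laboratory grades, so the primary objective is unaffected.

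**What to change.** - For the Day 90 and final analyses, set Templates 31–34 to Visit 2 (D7) up to Visit 5 (D90): in all four titles, in the column headers of Templates 31 and 33, and in the four template-list entries.
- State that the D7–D30 window serves the Day 30 analysis only.
- Align the Template 35 axis note with the figures planned for the Day 90 and final analyses, so that Days 60 and 90 are plotted.
- Check that the TFL table of contents for the Day 90 and final analyses carries the same window.

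The cost is a changed visit window in existing macros and some relabelling. No new data are needed, since the Day 60 and Day 90 samples are already scheduled for all subjects.

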
15-Mar-2018
	
Amendment 3: Description of changes from Amendment 2 are as below: For final analysis,
 
 – Some tables have been updated including removing to Annex, creating new corresponding in-text table by deleting or collapsing some columns/rows; – Two figures of ‘percentage of subjects reporting solicited local/general symptoms (any grade / grade 3) during the 7-day post-vaccination period’ have been newly generated for the final analysis, respectively; – The table of ‘Distribution of change from baseline in haematology and biochemistry with respect to normal laboratory ranges’ has been splitted and modified into three in-text tables for Alanine Aminotransferase (ALT)/ Aspartate Aminotransferase (AST)/Eosinophils, Creatinine/Lymphocytes/ White Blood Cells (WBC), Haemoglobin/platelet count/Neutrophils, separately; – Two new in-text tables of ‘Summary of haematology and biochemistry results by maximum grade in the specified category’ and ‘Summary of haematology change from baseline by maximum grade in the specified category’ have been generated; – Some figures of Individual results for each parameter have been modified. 	
Amendment 1 - 21-Aug-2017

---------------------------	--	---

01-Jun-2018
	
Amendment 4: Description of changes from Amendment 3 are as below: For final analysis
 
 – Many tables and figures have been moved between in-text and post-text; – Two figures of ‘percentage of subjects reporting solicited local/general symptoms (any grade / grade 3) during the 7-day post-vaccination period’ will be updated to include grade 2, respectively; – The parameter of BMI has been added in the table of ‘Summary of vital signs characteristics (Exposed set)’ and report at VISIT 1 (D0), MA-RTI VISIT 1 and MA-RTI VISIT 2; – This table of ‘Summary of haematology and biochemistry results by maximum grade in the specified category from VISIT 1 (D0) up to VISIT 2 (D7) (Exposed set)’ will be newly added for the final analysis in in-text; – Please check the dry run meeting minutes for the details 	
Amendment 1 - 21-Aug-2017

---------------------------	--	---

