- *The table of ‘Compliance in returning symptom information’ and all tables concerned with ‘Number and percentage of subjects taking a concomitant medication’ have been moved to Annex;*
- *The table of ‘Exploratory comparisons between groups in terms of percentage of subjects reported any Grade 2/3 AE and/or any fever >38.5°C and/or any vaccine-related SAE during the 7 day (Days 0-6) Post- vaccination period’ will not be reported in the final analysis;*
- *The table of ‘Distribution of change from baseline in haematology and biochemistry with respect to normal laboratory ranges’ has been moved to Annex; Three splitted in-text tables for ALT/AST /Eosinophils, Creatinine/Lymphocytes/White Blood Cells and Haemoglobin/ platelet count/ Neutrophils have been generated, separately;*
- *The table of ‘Summary of haematology and biochemistry results by maximum grade’ has been moved to Annex; One newly formatted in-text table of ‘Summary of haematology and biochemistry results by maximum grade in the specified category’ has been generated by collapsing the categories of unknown/grade 0 and grade 1 then renaming the new category of ‘other’, keeping grade 2, 3 and 4 column, and removing the column of n;*
- *The table of ‘Summary of haematology change from baseline by maximum grade’ has been moved to Annex; One newly formatted in-text table of ‘Summary of haematology change from baseline by maximum grade in the specified category’ has been generated by collapsing the categories of unknown/grade 0 and grade 1 then renaming the new category of ‘other’, keeping grade 2, 3 and 4 column, and removing the column of n;*

Changes in Amendment 4 mainly include the following.

Please check the dry run meeting minutes for details.

C.A.R.S./Clinical R&D/RSV F/Studies/021 (204812)/11 Statistics/11.05
General/11.05.03 Meeting Material/Analysis E01_01/RSV F-021 (204812) Dry Run
Minutes E01_01.

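### Templates 32 and 34 count Unknown subjects in the Other row but divide by subjects with available results, so Other is overstated and the rows can sum to more than 100%

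*SAP*

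**What the plan says.** The footnotes to Template 32 (haematology and biochemistry by maximum grade in the specified category) contain four definitions that have to work together:

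- header: "N = number of subjects with the administered dose"
- count: "n = number of subjects in the specified category"
- percentage: "n / Number of subjects with available results x 100"
- first row: "Other=all Unknown, Grade 0 and Grade 1"

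Template 34 (haemoglobin change from baseline) repeats all four. Section 9, under Amendment 3, shows that the merging was intended: the new tables come from "collapsing the categories of unknown/grade 0 and grade 1 then renaming the new category of" other.

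The table they were derived from, Template 31, is built differently. Unknown has its own column, and the footnote reads "N = number of subjects with at least one available result for the specified laboratory parameter and follow-up period".

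The Document History for Amendment 4 also lists a further table in the same specified-category format, covering Visit 1 (Day 0) up to Visit 2 (Day 7), which "will be newly added for the final analysis in in-text". Section 6.3.1.1 plans the post-vaccination maximum grade from Day 7 to Day 90, set against Day 0 as baseline, and Template 31 labels Day 0 as the PRE sample.

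**The concern.** A percentage needs its numerator to be a subset of its denominator. Here the Other row takes in subjects whom the denominator leaves out. Two things follow: the Other percentage is inflated, and subjects without a result are shown in one figure with subjects whose result was Grade 0 or 1.

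Laboratory abnormality is a listed secondary endpoint (Section 4.2), and Amendment 3 put the collapsed tables in the body of the report while moving the full table to the Annex. A reader of the report text would see a row that can print above 100%, and could not tell from that table how much of the apparently low-grade share is missing data.

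The Day 0 to Day 7 table raises a separate question of interpretation. If it shows only the maximum over both visits, a Grade 2 value present before vaccination and resolved by Day 7 would appear as that subject's grade, and could be read as a post-vaccination finding.

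**Working it through.** **Inputs.** The definitions come from the footnotes to Templates 32 and 34. The group size of about 100 is in Section 2, Table 1. The number unknown is not given anywhere in the SAP, so 0 to 10 per 100 is an assumption. The SAP states no percentage of its own to reproduce.

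**Notation.** N = subjects dosed, U = unknown, A = N - U = subjects with available results, g = subjects with maximum Grade 2, 3 or 4.

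**Formulas from the footnotes.**

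- Other count = U + (A - g) = N - g
- Other % as written = (N - g)/A
- Other % with Unknown removed = (A - g)/A
- Overstatement = U/A
- Grade 2 to 4 % = g/A, unaffected by U being in Other
- Sum of rows = (N - g + g)/A = N/(N - U)
- Other alone exceeds 100% only if N - g > A, that is, if U > g

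**Results for N = 100.**

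| U | g | A | Other % as written | Grade 2 to 4 % | Sum | Other % without Unknown |
|---|---|---|---|---|---|---|
| 0 | 2 | 100 | 98.0 | 2.0 | 100.0 | 98.0 |
| 1 | 2 | 99 | 99.0 | 2.0 | 101.0 | 98.0 |
| 2 | 2 | 98 | 100.0 | 2.0 | 102.0 | 98.0 |
| 5 | 2 | 95 | 103.2 | 2.1 | 105.3 | 97.9 |
| 5 | 5 | 95 | 100.0 | 5.3 | 105.3 | 94.7 |
| 10 | 2 | 90 | 108.9 | 2.2 | 111.1 | 97.8 |

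The printed N is the sum of the n column (U + Grade 0/1 + Grades 2 to 4 = N). The counts are therefore coherent with N; only the divisor differs.

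**Day 0 to Day 7 table.** With a Grade 2 or higher rate of b at Day 0 and p at Day 7, and independence assumed between them, the share with a maximum of Grade 2 or higher is 1 - (1 - b)(1 - p). For an assumed p of 3%:

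- b = 1%: 1 - 0.99 x 0.97 = 4.0%
- b = 3%: 1 - 0.97 x 0.97 = 5.9%
- b = 10%: 1 - 0.90 x 0.97 = 12.7%

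Day 7 alone would show 3%. Abnormalities that persist from Day 0 to Day 7 would make the gap smaller than under independence. These rates are illustrations only.

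**The case against.** Several points on the other side stand.

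- The rows that carry the safety signal are right. Grades 2, 3 and 4 are divided by subjects with available results. A reader might infer that every percentage is wrong once a result is missing; the footnotes do not support that.
- Other does not always exceed 100%. It does so only when unknowns outnumber Grade 2 to 4, and with no unknowns nothing is wrong.
- Missing results are not hidden across the report. Templates 30 and 31 keep Unknown separate, and the full tables were moved to the Annex, not dropped.
- Template 32 as drawn spans Day 7 to Day 30, so a subject is unknown only with no result at either visit. Ten per 100 is a high illustration.
- Amendment 4 says many tables moved between in-text and post-text, so the final placement of Templates 32 and 34 is not certain.
- Annex 4 calls its displays and footnotes illustrative and allows minor changes. The tables are descriptive and do not enter the desirability index.

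One point is open. The SAP does not define Unknown. Template 31 has an Unknown column although its N is restricted to subjects with a result, which could mean available but not gradable. On that reading the rows would sum to 100%, though ungraded results would still be merged with Grades 0 and 1. Because Templates 32 and 34 take dosed subjects as N and put all Unknown in Other, no result is the plainer reading.

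On the Day 0 to Day 7 table, a reader might infer a contradiction with Section 6.3.1.1. The documents do not show one. The Day 7 to Day 90 analysis against baseline remains planned, the new table is an addition to it, and Section 4.2 itself lists Day 0 among the endpoint time points. The table is known only from its title in the Document History: Annex 4 has no template for it, and Section 9 refers to meeting minutes that are not part of the SAP.

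**Conclusion.** The footnotes of Templates 32 and 34 do not fit together, and applied literally they give a wrong number. The Other percentage is overstated by U/(N-U), which is 2.0, 5.3 or 11.1 percentage points for 2, 5 or 10 unknown per 100 dosed, and the rows sum to 102.0%, 105.3% or 111.1%. This rests on reading Unknown as no result and on assumed missing counts. The error is confined to the Other row and the column total.

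The Day 0 to Day 7 table is a matter of clarity, not a demonstrated error. Its stated window includes the pre-vaccination sample, and the SAP does not show how baseline and post-vaccination grades would be told apart.

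**What to change.** In Templates 32 and 34:

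1. Define Other as Grade 0 and Grade 1 only.
2. Show Unknown as a separate count without a percentage, and state what it means.
3. Print as N the number of subjects with at least one available result in the window, as in Template 31, and use it as the denominator. Because availability can differ between parameters, N belongs beside each parameter and not in the group header.

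Dividing everything by subjects dosed would also bring the sum to 100% (98.0% and 2.0% with U = 5 and g = 2), but it would leave missing subjects merged with Grades 0 and 1, so it is the weaker repair.

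For the table added in Amendment 4, tabulate the Day 7 grade against the Day 0 grade, in the style of Template 31, and include that layout in Annex 4.

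The cost is a few footnotes, one extra row and a small macro change. No new data are needed, and the footnote changes look to be within what Annex 4 allows without a further amendment.
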